4.1. Changes From Analyses Specified in the Protocol

Not applicable. There are no changes from the protocol.

4.2. Changes From Analyses Specified in the Previous Version of the Statistical Analysis Plan

Not applicable. This is the first version of the SAP.

5. DEFINITIONS

5.1. Efficacy

There are no efficacy assessments performed during this study.

5.2. Copper and Molybdenum Balance Measurements

Copper and Mo balance measurements will be made on all intake (ie, study drug, food, and fluids) and all output (urine and feces) from participants as indicated in the SoA. The Cu and Mo concentration of each sample will be determined by inductively coupled plasma mass spectrometry (ICP-MS). Copper and Mo content of all intake and output will be calculated based on the volume or weight of intake and output and the concentration of representative samples.

5.2.1. Primary Objective and Endpoint

The primary objective of this study is to assess change from Baseline in Cu balance over 2 weeks of repeated daily ALXN1840 dosing. The primary endpoint is the change in mean daily Cu balance from pretreatment Baseline Period to ALXN1840 Treatment Period, as measured by the calculated difference between Cu intake (in food and drink), and Cu output (in feces and urine).

5.2.1.1. Food and Fluid Collection for Copper and Molybdenum Concentrations

Samples of all meal and fluid batches will be collected and analyzed for measurement of Cu and Mo content. A minimum of 3 complete portions/meals from each food and liquid batch will be sent for analysis. All participants will drink water from the same large water bottle dispenser. Samples of water from this dispenser will be collected and analyzed for Cu and Mo content.

Samples will be collected, stored and shipped as detailed in the Laboratory Manual. Copper and Mo concentration of each food sample (ng/g) and each fluid sample (ng/mL) sample will be determined by ICP-MS.

5.2.1.2. Urine Collection for Measurement of Copper and Molybdenum Content

Urine samples to measure Cu and Mo content will be taken from Day -4 through Day 30, as described in the SoA ([Protocol Table 1](#)). Samples will be collected, stored and shipped as detailed in the Laboratory Manual. For each 24-hour collection period, urine will be pooled for analysis and volumes will be recorded.

Copper and Mo concentration (ng/mL) of each 24-hour urine sample will be determined by ICP-MS.

5.2.1.3. Fecal Collection for Measurement of Copper and Molybdenum Content

Fecal samples to measure Cu and Mo content will be taken from Day -4 through Day 30 as described in the SoA ([Protocol Table 1](#)). Samples will be collected, stored and shipped as detailed in the Laboratory Manual. Fecal samples will be individually collected, weighed and stored. The weight and time of each bowel movement will be recorded.

Copper and Mo concentration (ng/g) of each stool sample will be determined by ICP-MS; each sample will be analyzed using a minimum of technical triplicates.

5.2.2. Secondary Objectives and Endpoints

The secondary objectives and endpoints are:

| Objectives | Endpoints |
|--|--|
| Assess net copper (Cu) balance over 2 weeks of repeated daily ALXN1840 dosing | Mean daily Cu balance during ALXN1840 Treatment Period where Cu balance is measured by the calculated difference between Cu intake (in food and drink), and Cu output (in feces and urine) |
| Assess steady-state molybdenum (Mo) balance after 2 weeks of repeated daily ALXN1840 dosing | Mean daily Mo balance at ALXN1840 pharmacokinetic (PK) steady state, as demonstrated through measurement of Mo intake (in food, drink, and ALXN1840), and Mo output (in feces and urine) |
| Assess extent of Mo excretion in urine and feces | Quantify total Mo excretion in urine and feces following ALXN1840 treatment compared with Baseline |
| Determine the steady-state plasma PK of ALXN1840 after 2 weeks of repeated daily ALXN1840 dosing | PK parameters for plasma total Mo and plasma ultrafiltrate (PUF) Mo including terminal elimination for Mo after steady-state dosing |
| Investigate the effect of ALXN1840 on the disposition of Cu after 2 weeks of repeated daily ALXN1840 dosing at steady state | Cu quantified in food, feces, and urine over 2 weeks of ALXN1840 dosing including plasma total and labile bound Cu (LBC) at steady state |
| Investigate the effect of ALXN1840 on the disposition of Cu over 2 weeks of repeated daily ALXN1840 dosing and through the Post-treatment Period | Cu quantified in food, drink, feces, and urine |
| Investigate the effect of ALXN1840 on the disposition of Mo over 2 weeks of repeated daily ALXN1840 dosing and through the Post-treatment Period | Mo quantified in ALXN1840 doses given and in food, drink, feces, and urine |

5.2.3. Exploratory Objectives and Endpoints

The exploratory objectives and endpoints are:

| Objectives | Endpoints |
|--|--|
| Assess the effects of ALXN1840 on ceruloplasmin (Cp), ceruloplasmin-bound Cu (CpC), and labile bound copper (LBC) profiles in plasma | Absolute and percent changes in Cp, CpC, CpC:Cp ratio, and LBC during Treatment Period and post-treatment compared with predose Baseline |
| Assess the effects of repeated daily ALXN1840 dosing on Cu:Mo ratio in plasma at steady state | Measure plasma Cu:Mo ratios during Treatment Period and post-treatment compared with predose Baseline |
| Assess the effects of ALXN1840 on Cu:Mo ratio in urine and feces | Measure the average daily Cu:Mo ratio in urine and feces during treatment and post-treatment compared with predose |
| Assess the effects of ALXN1840 on the time course of Cu balance over 2 weeks | Evaluate the effect of time on change in average daily Cu balance |

5.3. Safety

The safety objective of this study is to evaluate the safety and tolerability of repeated dose administration of ALXN1840 in healthy participants. Treatment-emergent adverse events (TEAEs)/serious adverse events (SAEs), clinical laboratory assessments (serum chemistry, hematology, coagulation, and urinalysis), and physical examinations will be evaluated. Heart rate, intervals (PR, QRS, interval between the start of the Q wave and the end of the T wave in an electrocardiogram (ECG) (QT), and QT interval corrected [QTc]), clinically significant ECG findings as determined by triplicate 12-lead ECG will be assessed, and vital sign assessments

(body temperature, blood pressure, respiratory rate and heart rate) will be measured. The SoA is provided in [Table 1 of the Protocol](#).

5.3.1. Adverse Events

All AEs will be reported to the Investigator or qualified designee by the participant (or, when appropriate, by a caregiver, surrogate, or the participant's legally authorized representative).

All AEs and SAEs will be collected from the signing of the informed consent form (ICF) until the End of Study (EOS) Visit.

Each AE will be characterized (ie, verbatim term) and information regarding its seriousness, start and stop dates, toxicity, outcome, and causal relationship with the study drug will be provided. The safety evaluation will include an assessment of all AEs, SAEs, AE toxicity, and AE relatedness to study drug. Adverse event toxicity will be evaluated using the National Cancer Institute (NCI) Common Terminology Criteria for Adverse Events (CTCAE) Version 5.0 (published 27 Nov 2017) ([NCI, 2017](#)). Further details are given in the [Protocol Section 8.3](#) and [Protocol Appendix 3](#).

5.3.2. Laboratory Assessments

Clinical laboratory measures include chemistry, hematology, coagulation, urinalysis and other tests.

Participants' bowel movements and urination will be monitored by the clinical staff. The clinical staff will record each time a fecal and urine sample is collected in the case report form (CRF).

To support accurate quantification of Cu/Mo intake, each participant's intake including both food and fluids will be monitored and recorded. Following each standardized meal, the clinical staff will record 100% completion of each meal including all liquids. If a participant is unable to eat 100% of the food for a given meal, the remaining food will be weighed and reported in the CRF to support accurate determination of Cu/Mo as a fraction of the total meal. Similarly, if participants do not complete 100% of non-water fluids with meal, the remaining volume will be measured and recorded in the CRF. In the case of water intake, the staff will record daily water volume intake in the CRF.

Clinically significant laboratory values are those deemed by the Investigator to be clinically significant resulting in further evaluation or treatment or those associated with an AE or clinical signs or symptoms. All laboratory test results with values considered abnormal and clinically significant during participation in the study after the last dose of study drug should be repeated until the values return to normal or Baseline or are no longer considered clinically significant by the Investigator or medical monitor.

The specific laboratory assessments are provided in [Section 10.2 of the Protocol](#).

5.3.3. Vital Signs

Vital signs will be measured in a semi-supine position after a five-minute rest and will include body temperature, heart rate (beats/min), respiratory rate, and systolic and diastolic blood pressure (mmHg). Readings will consist of a single pulse and blood pressure measurement. If vital signs are abnormal as defined by inclusion/ exclusion criteria, 2 additional vital signs

measurements will be made. The mean of the 3 vital signs measurements will be recorded in the CRF and used to determine participant eligibility.

5.3.4. Physical Examinations

A complete physical examination will include, at a minimum, assessments of the cardiovascular, respiratory, gastrointestinal, and neurological systems. Height (at Screening only) and weight (as per the SoA for physical examinations) will also be measured and recorded. A symptom-driven physical examination may be performed at other times, at the Principal Investigator's discretion.

5.3.5. Electrocardiograms

Triplicate 12-lead ECGs will be conducted as outlined in the SoA (**Protocol Table 1**) to obtain heart rate, PR interval, RR interval, QRS duration, QT interval, and QTc interval. If ECG interval measurements are abnormal, an additional 2 replicate measures will be performed with the mean of the 3 measured interval values used to confirm eligibility and recorded in the CRF.

5.4. Pharmacokinetics and Pharmacodynamics

5.4.1. Pharmacokinetics

Whole blood samples will be collected for the measurement of plasma concentrations of total and plasma ultrafiltrate (PUF) Mo as specified in the SoA via ICP-MS. Samples will be used to evaluate the PK of ALXN1840. Samples collected for analyses of plasma concentrations may also be used to evaluate safety aspects related to concerns arising during or after the study. The actual date and time (24-hour clock time) of each sample will be recorded.

5.4.2. Pharmacodynamics

Plasma total Cu, Cp, CpC, PUF Cu, non-ceruloplasmin-bound Cu (NCC), and labile bound Cu (LBC) will be assessed during the study.

Blood samples will be collected as described in the SoA (**Protocol Table 1**) for plasma isolation as per the Laboratory Manual. The isolated plasma will be stored at -20°C before analysis. Plasma samples will be used for ICP-MS measurement of total Cu, Cp, CpC, PUF Cu, and toxic Cu as measured by LBC and/or NCC at the time points indicated in the SoA.

6. DATA SETS ANALYZED (STUDY POPULATIONS)

6.1. Screened Set

All participants who signed the ICF.

6.2. Enrolled Set

All participants who signed the ICF, were eligible for the study, and were registered on Day -7.

6.3. Full Analysis Set

All participants who received at least 1 dose of ALXN1840. The primary analysis will be performed using the Full Analysis (FA) Set.

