4. DESCRIPTION OF THE PROTOCOL

Study ALXN1840-HV-108 is a single-arm, open-label, repeat-dose (30 mg/day) study designed to assess the effects of ALXN1840 administration on copper (Cu) balance in healthy participants.

Approximately 17 participants will be enrolled and will receive study drug to achieve 13 evaluable participants who complete the study (Appendix 9.1). This study will be conducted in a minimum of 2 groups. The first group will consist of approximately 6 participants and no more than 8 participants. The second group may only be initiated after the Safety Review Committee (SRC; defined in Section 9.7 of the Protocol) reviews safety information (all adverse events [AEs], safety laboratory data, and vital signs) through Day 18 and agrees that it is safe to continue enrollment to complete the study. If ceruloplasmin (Cp) concentrations or AE findings are suggestive of over-depletion of Cu, the SRC may propose a dose reduction to 15 mg/day for the remainder of the study population.

This is a single arm study. Following Screening and enrollment, participants will have a Run-in Period to support diet equilibration (Day -7 through Day -5) and measurement of pretreatment Cu and molybdenum (Mo) balance (Day -4 through Day -1). Following the Run-in Period, participants will be administered ALXN1840 at 30 mg/day for 15 days (Day 1 through Day 15). ALXN1840 will be administered orally after an overnight fast, and participants will remain fasted for a minimum of 2 hours following each dose administration. Following completion of the 15-day dosing period, participants will remain the clinical research unit (CRU) for an additional 16 days until discharge on Day 31. The study design schematic is presented in Figure 1.

Figure 1: Study Design Schematic

Participants will be admitted to the CRU on Day -8 and discharged on Day 31.

Participants eligible for the study will be enrolled (assigned a subject number) on Day -7. A Cu- and Mo-controlled diet will be initiated on Day -7 and will be continued through Day 30.

Participants will be administered ALXN1840 at a dose of 30 mg/day from Day 1 through Day 15, with the Post-treatment Period starting at Day 16.

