7. STATISTICAL ANALYSIS

Summary statistics will be computed and displayed by day and period (pre-dose Baseline, treatment, steady state, and post-treatment), where applicable. Descriptive statistics for continuous variables will minimally include the number of participants, mean, standard deviation (SD), minimum, median, and maximum. For categorical variables, frequencies and percentages will be presented. Graphical displays will be provided as appropriate.

Analyses will be performed using the SAS[®] (Statistical Analysis Software[®]) software Version 9.4 or higher (SAS Institute Inc., Cary, North Carolina).

In general, analyses will be presented by group (referring to the study being conducted in groups; see Section 4) and overall, where specified.

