7.3. Copper and Molybdenum Balance Analyses

The primary objective of this study is to assess the change from Baseline in Cu balance over 2 weeks of repeated daily ALXN1840 dosing (ALXN1840 treatment at 30 mg/day in healthy participants). Secondly, the study will also assess whether a net negative Cu balance is achieved following ALXN1840 treatment. The study will also assess Mo balance at ALXN1840 PK steady state.

Copper balance is defined by the difference in Cu input and Cu output. A negative Cu balance will indicate greater Cu output than Cu intake. Copper input is defined as the sum of all Cu input as measured in all food and fluids over the specified period. Copper output will be defined as the sum of all Cu output as measured in urine and feces over the specified collection period. Many of the Cu inputs and outputs will be collected with technical replicates and the mean of the replicates will be utilized in the analysis. Daily balance values may also be calculated. The study assumes insensible Cu/Mo loss due to sweat does not change significantly with ALXN1840 treatment and is therefore not measured.

Molybdenum mass balance is defined as the difference in Mo input and Mo output. It will be calculated in a similar manner as Cu balance and includes the additional Mo intake from ALXN1840. The nominal amount of Mo contained in ALXN1840 will be used and is estimated as 3.33 mg in each 15 mg tablet per the following calculation: 95.96 g/mol (molecular weight of Mo) / 432.54 g/mol (molecular weight of bis-choline tetrathiomolybdate) * 15 mg/tablet = 3.33 mg Mo. Mo mass balance will be calculated at steady state (Day 12 through Day 15) and over the entire Treatment Period (Day 1 through Day 30).

The average daily Cu and Mo balance, and/or change from Baseline in average daily Cu and Mo balance will be calculated using data from the following periods:

- Day -4 through Day -1 representing the Pre-dose Baseline Period (Cu/Mo balance)
- Days 4 through Day 15 representing the 30 mg/day Treatment Period (Cu balance for primary and secondary endpoints)
- Day 1 through Day 15 representing the ALXN1840 30 mg/day Treatment Period (Mo mass balance and Cu as exploratory analyses)
- Days 12 through Day 15 representing the Steady State Treatment Period (steady state Mo/Cu balance)
- Days 1 through Day 30 representing the entire Treatment and Post-treatment Period (total Mo and Cu balance)

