7.3.1. Primary Analysis

The primary analysis will be performed using the FA Set. Additionally, the primary analysis will be performed on the PP Set. Change from Baseline in average daily Cu balance over Days 4 to 15 will be summarized using descriptive statistics based on data as observed. The 95% confidence limits for the mean change from Baseline will be provided.

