7.3.2. Secondary Analyses

Secondary analyses will be performed using the FA Set. The secondary continuous endpoints (Cu balance, Mo balance, urinary excretion, etc.) will be analyzed using the same methods described for the primary analysis. The periods of interest described in Section 7.3 will be utilized as appropriate. The daily Cu and Mo balances for each participant will be plotted, as will the mean daily Cu and Mo balances.

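### If the dose were cut to 15 mg/day after the first group, would the copper-balance results mix two doses under a 30 mg/day label?

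*SAP*

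**What the plan says.** The primary analysis set is everyone dosed, at any dose level (SAP 6.3): "All participants who received at least 1 dose of ALXN1840. The primary analysis will be performed using the Full Analysis (FA) Set". On that set, SAP 7.3.1 plans one kind of result: "Change from Baseline in average daily Cu balance over Days 4 to 15 will be summarized using descriptive statistics based on data as observed", with 95% confidence limits for the mean. SAP 7.3.2 carries this over: "The secondary continuous endpoints (Cu balance, Mo balance, urinary excretion, etc.) will be analyzed using the same methods described for the primary analysis". The window is named in SAP 7.3: "Days 4 through Day 15 representing the 30 mg/day Treatment Period (Cu balance for primary and secondary endpoints".

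The same SAP allows for a second dose level. Section 4 says that if ceruloplasmin or adverse-event findings point to copper over-depletion, "the SRC may propose a dose reduction to 15 mg/day for the" participants still to be treated. It also fixes the order of events: "The second group may only be initiated after the Safety Review Committee" has reviewed the first group's data through Day 18.

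The presentation rule is at the head of SAP 7: "In general, analyses will be presented by group (referring to the study being conducted in groups; see Section 4) and overall, where specified". The expected course is a single dose for all (Protocol 6.3, SAP 9.1).

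**The concern.** Nothing in SAP 7.3.1 or 7.3.2 says how copper balance is summarised if two doses are given. The other places where such a rule might stand do not supply it. The Per Protocol Set names no dose level (SAP 6.4), and no subgroup or sensitivity analysis is planned (SAP 7.3.1.2 and 7.3.1.5). The protocol, by contrast, does foresee an affected dose group in its stopping rules (Protocol 6.6.1.3).

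Read literally, a reduction after the first group could lead to one mean and one interval on the Full Analysis Set that combine 30 and 15 mg/day under a 30 mg/day heading. No error rate is at stake, because no hypothesis is tested (SAP 7.3.1.4). What could suffer is the reading of a descriptive estimate: a mixture taken for the effect of 30 mg/day.

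**Working it through.** **1. Sample size.** From SAP 9.1: 13 evaluable, 25% dropout. 13/(1 − 0.25) = 17.3 and 17 × 0.75 = 12.75, so the stated figure of about 17 enrolled is reproduced.

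**2. What pooling could do.** Inputs: first group of 6 to 8 (SAP 4); N = 17 dosed, or N = 13 evaluable with the first group assumed fully retained. Let r be the ratio of the 15 mg effect to the 30 mg effect. The documents give no value for r, so it is an assumption, shown from 0 to 1.

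Pooled effect ÷ 30 mg effect = (n30 + r × n15)/N. Example: (6 + 0.5 × 11)/17 = 11.5/17 = 0.68.

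| N | n30 | n15 | Share at 15 mg | Mean assigned dose (mg/day) | r = 0 | r = 0.5 | r = 1 |
|---|---|---|---|---|---|---|---|
| 17 | 6 | 11 | 65% | 20.3 | 35% | 68% | 100% |
| 17 | 8 | 9 | 53% | 22.1 | 47% | 74% | 100% |
| 13 | 6 | 7 | 54% | 21.9 | 46% | 73% | 100% |
| 13 | 8 | 5 | 38% | 24.2 | 62% | 81% | 100% |

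A pooled figure could therefore be anything from unchanged to well diluted. The spread comes from the assumed r, not from evidence in the documents.

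**3. Would the tables pool?** The SAP 7 sentence can be read in two ways. Either by-group is the default and an overall column is added where specified, or both appear only where specified. The SAP's own usage favours the first reading. Compliance is given by group alone (SAP 7.4.1), while demographics, laboratory tests and vital signs add an overall summary explicitly (SAP 7.1.3, 7.4.3.1, 7.4.3.2). On that reading, silence in 7.3.1 and 7.3.2 leaves by-group results in place.

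**4. Would group equal dose?**
- First group: last dose on Day 15.
- SRC review: data through Day 18, so at least 3 days after that last dose.
- Second group: starts only after the review.

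The reduction described would leave the first group wholly at 30 mg/day and everyone later at 15 mg/day. If there were more than two groups, each would still have one dose, so no by-group column would mix doses.

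**5. Could a dose change within a group?** Protocol 6.6.1.2 to 6.6.1.5 stop or suspend dosing; none describes a within-group reduction. After a suspension, the study continues only under an approved protocol amendment (Protocol 6.6.1.3 and 6.6.1.6), which is the natural time to revise the SAP. Protocol 6.6.1.6 does mention dose modification in general terms, so the case is remote but not excluded.

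**6. Precision if doses are separated.** The 95% half-width in SD units is t(0.975, n − 1)/√n: 1.05 for n = 6, 0.84 for n = 8, 0.60 for n = 13 and 0.51 for n = 17. Single-dose intervals would be wider whatever the SAP's wording.

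**The case for a change.** The strongest case for a change is that the sponsor wrote the reduction into the plan and then did not follow it through to the primary endpoint. The phrase about where results are specified is ambiguous, and a reader could hold that no by-group copper table is required. Even with one, the SAP does not say which number is the headline result, and the 30 mg/day window label would be wrong for anyone on 15 mg/day. The between-group reduction, unlike a suspension, carries no stated need for a protocol amendment. In an open-label study the choice of headline could therefore be made after the first group's data are seen. The remedy would cost only a few lines.

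Part of this stands. The contingency rule is not written down, and the label describes the planned regimen whatever is given. But the formal primary objective and endpoint (SAP 5.2.1) name no dose; the 30 mg/day wording belongs to the analysis narrative in SAP 7.3. Retitling a table after a dose change is ordinary reporting. A mixture could not pass unnoticed either: "The daily Cu and Mo balances for each participant will be plotted", and SAP 7.4.1 summarises average, minimum and maximum daily dose. Those outputs give no mean or interval by dose, but they would prompt any analyst to produce one. SAP 6.3 itself needs no correction, since it only defines a set.

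**Conclusion.** The point does not call for a change. It arises only if the SRC makes a reduction that the plan does not expect. Even then, the general by-group rule, together with the timing of the Day 18 review, would already separate the doses. What is left is missing detail that analysts would supply sensibly: show copper balance by dose received, and name any pooled figure as such.

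This rests on two assumptions: that by-group presentation is the default in SAP 7, which is the more natural reading but not the only one, and that any reduction falls between groups, as the plan describes. The size of any dilution is unknown. The 68–81% range depends wholly on an assumed half effect at 15 mg/day, and it becomes 100% if the effects are equal. No test, error rate or power figure is affected, and no view is taken on dose.
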